5.0 Background Information on Treatment Modalities and Correlative Studies

5.1 Background on Treatment Modalities

Intensity modulated radiotherapy uses photon beams to deliver treatment. The advantage of this treatment modality over traditional or 3D-conformal radiation lies in increasing dose conformality. By dividing each radiation field into a number of separate beamlets, using inverse planning and intensity modulation, and then adding beamlets together to form a cumulative dose distribution the treatment can be highly sculpted to the tumor. In multiple tumor types this technique has been shown to greatly reduce side effects while maximizing tumoricidal doses to the target. However, this technique is constrained by the physical properties of photons. Photons deposit dose as they travel through normal tissues both upon entrance and exit after passing through the target. As multiple beam angles are used, one criticism of IMRT is the "low dose bath" that surrounding normal tissues receive. While IMRT is a substantial improvement over conventional or even 3D techniques and is now the standard for irradiation of glioblastoma at our institution, IMPT may be even more advantageous.

Intensity modulated proton therapy is also a method of delivering ablative doses to the primary tumor while minimizing radiation to surrounding normal structure. The basis of the advantage of protons over photons in general lies in their action in exposed tissues. Specifically, in contrast to photons which are absorbed throughout the course of their beam path, protons have a finite range of action that is dependent on the initial proton energy. Protons traverse most of the beam path and then deposit their energy near the target in the Bragg peak with little or no exit dose. When several beams of closely spaced energies are combined a spread-out Bragg peak (SOBP) can be created which results in a modulated proton beam. In IMPT there is simultaneous optimization of all Bragg peaks from all incident beams. This ability to modify treatment voxel by voxel results in increased dose conformality. IMPT was pioneered at the Paul Scherrer Institute in Switzerland but is now being offered commercially by Varian Medical Systems (Palo Alto, CA). IMPT has been proposed as being most useful in treating complex field shapes such as brain tumors.

In short, IMRT and IMPT have many similarities. Both involve the delivery of fractionated, daily radiation to targeted brain tissues although they accomplish this with different modalities. In both treatment types radiation is highly targeted to specific sites in the brain to include gross residual disease as well as areas at high clinical risk of microscopic disease. However, as delineated above there are differences between the two treatment modalities. In particular the decreased exit and low doses to normal structures with IMPT suggest that there may be a significant difference between the two modalities in regards to cognitive outcomes. However, there is an increased cost associated with IMPT and as stewards of our healthcare system it is important to show if there is a measurable clinical benefit associated with the use of IMPT.

5.2 Background for correlative studies

5.2.1 Genetic Markers

Apolipoprotein E (ApoE) is an important factor in remodeling and repairing neurons in response to injury or stress through its lipid transport function. In fact, recent data suggests that patients having the Apo E4 isoform realize Alzheimer's dementia far earlier than those without it [22]. This allele is present in 16% of the general population and 50% of patients with late onset Alzheimer's dementia [23]. Given the similar mechanisms of dementia between Alzheimer's dementia and radiation induced dementia (e.g. vascular or metabolic), Apo E4 genotyping may prove to be a predictor of radiation induced neuronal damage. The Apo E4 protein binds rapidly and tightly to beta amyloid. Normally beta amyloid exists in a soluble form. However, when bound by Apo E4 protein, beta amyloid becomes insoluble and is more likely to be deposited in plaques which may lead to changes in microvasculature, ultimately leading to neurocognitive decline. Further, patients with just one copy of the Apo E4 allele have demonstrated accelerated hippocampal volume loss which can also compromise neurocognitive function [24]. Recent preclinical mouse data from Crawford and Villasana have shown neurogenesis in the hippocampus and hippocampal dysfunction depending on Apo E status [25, 26]. Patients with Apo E2 and Apo E3 alleles, on the contrary, tend to have one quarter the risk of developing Alzheimer's disease. It is felt that the E2 and E3 alleles are able to facilitate repair and protection from neuronal damage. Apo E genotyping will be performed to assess whether a subgroup of patients exists that is genetically predisposed to developing neurocognitive decline (or neuroprotection).

5.2.2 Inflammatory Markers

Markers of inflammation are elevated with aging and their increase has been associated with cognitive decline [27, 28]. Epidemiological and retrospective data reveals an improvement in neurocognitive function with the use of NSAIDs in patients with Alzheimer's dementia, supporting an inflammatory process involved in neurocognitive decline [23]. Chronic inflammation as a result of mass effect from tumor or treatment related inflammation may be associated with neurocognitive deficits and can be measured in plasma. Interleukin 1 (IL-1), Interleukin 6 (IL-6), and Tumor Necrosis Factor alpha are pro-inflammatory cytokines that are a measure of inflammation and have been shown to be elevated in patients with Alzheimer's dementia [29-32]. In this study, inflammatory biomarkers will be measured at baseline (after registration, but prior to treatment) and at each follow-up visit when neurocognitive testing is performed.

5.2.3 Hormone and Growth Factors

Aging and memory decline is associated with the disruption of hormone regulation, including glucocorticoids, gonadal steroids, and growth hormone [33]. Cortisol, human chorionic gonadotropin (hCG), insulin-like growth factor-1

(IGF-1), and neuronal growth factor (NGF), have all recently been associated with cognitive decline in Alzheimer's disease [34, 35]. ELISA testing of serum specimens for each hormone and growth factor will be performed at baseline (after registration, but prior to treatment) and at each follow-up visit when neurocognitive testing is performed.

5.2.4 Molecular Clinical Prognosticator (MCP)

Classification according to both molecular biomarkers and the well-validated Glioma RTOG recursive partitioning analysis (RPA) classification [36, 37] is important for accurate survival prediction. Robust survival classification are important both in planning randomized trials for stratification and for selection of patients for appropriate therapy. In order to increase the survival classification resolution while minimizing the impact on patient enrollment requirements, we have developed a new prognostic classifier, the MCP. The MCP was developed using methodologies suitable for archival, formalin-fixed, paraffin-embedded (FFPE) tissue. In its development, a generalized "training and validation" approach was used in which the statistical model was built on a set of cases to optimize survival class discrimination (training set) and a subsequent, blinded and independent cohort was used to validate this model (validation set). The training set consisted of approximately 250 GBM specimens that were then validated using 725 specimens obtained prospectively as a requirement for randomization in the RTOG 0525 trial. It is thus a fully validated prognostic classification scheme.

The MCP consists of 4 molecular components each of which is an independent prognostic marker after adjusting for RTOG RPA class. First, we include a comprehensive, 10 assay analysis of the *MGMT* promoter which more robustly predicts outcome compared to the standard single assay used in prior glioma trials [38]. Second, refinement of a gene expression (mRNA) classifier based on 19 genes that expands on a prior mRNA-based gene predictor [39]. Third, we have incorporated *IDH1* mutation status, a well-known genetic prognostic marker in gliomas [40]. As a fourth and final molecular component, an optimal set of gene promoters from the glioma CpG Island Methylator Phenotype (G-CIMP) [41] signature was selected to include 6 gene assays. Patients are divided in 1 of 3 risk groups based on the number of methylated sites.

The combination of these 4 molecular classifications resulted in 72 possible risk groups (the product of 3 *MGMT*, 4 mRNA, 2 *IDH1*, and 3 CIMP) that were then subjected to classification partitioning resulting in 4 molecular-prognostic (MP) groups. These 4 MP groups were then combined with the 3 RTOG RPA classes (12 risk groups total, the product of 4 MP and 3 RPA) and partitioned again into 4 resulting molecular-clinical prognostic (MCP) classes. The MCP

provides robust survival classification of patients with GBM. We propose to further validate it using patients from the current trial.

6.0 Patient Eligibility

Inclusion Criteria:

- 6.1 All patients must have histological proof of glioblastoma or gliosarcoma (WHO Grade IV) adapted RPA class III, IV, or V.
- 6.2 All patients must be ≥ 18 years of age.
- 6.3 All patients must sign informed consent verifying that they are aware of the investigational nature of this study in keeping with the rules and policies of M.D. Anderson Cancer Center. The only acceptable consent form is the one approved by M.D. Anderson IRB.
- 6.4 All patients must have a baseline Mini Mental Status Examination score \geq 21.
- 6.5 All patients must have a KPS \geq 70.
- 6.6 All patients must be eligible to have either IMRT or IMPT as determined by the study radiation oncologist.
- 6.7 All patients must be able to undergo MRI with and without contrast with a glomerular filtration rate (eGFR) greater than or equal to 30 mg/min/1.72 m².
- 6.8 All patients must have adequate liver, renal, and hematologic function within 14 days of registration as defined by Aspartate Amino Transferase (AST)/Alanine Amino Transferase (ALT)/Alkaline Phosphatase < 3 times normal, creatinine \leq 1.7 mg/dl, BUN \leq 35mg/dl, absolute neutrophil count \geq 1,800 cells/mm³, Hemoglobin \geq 10 g/dl, and platelet count > 100,000.
- 6.9 All patients must be able to adequately read, write and speak to participate in the cognitive and quality of life assessments. However mild to moderate deficits in these functions due to tumor are allowed.

Exclusion Criteria:

- 6.10 Patients will be excluded if they are not planning to receive concurrent temozolomide.
- 6.11 Patients will be excluded if they have had prior radiation to the brain.
- 6.12 Patients will be excluded if they have had prior surgical resection of brain for other brain tumors.
- 6.13 Patients will be excluded if they are pregnant as assessed by serum b-HCG. A serum b-HCG test will be performed no greater than 14 days prior to study registration for women of childbearing potential.
- 6.14 Patients with gliomatosis will be excluded.
- 6.15 Patients with Glialdel (BCNU) implanted wafers will be excluded.
- 6.16 Patients weighing greater than 136 kilograms will be excluded.

7.0 Treatment Plan

- 7.1 Eligible patients will be randomized in equal numbers to each treatment arm using CORe. Randomization will be stratified using the following factors:7.1.1 RPA class (III or IV vs. V)
 - 7.1.2 Mini Mental Status Examination score (21-26 vs. 27-30)
 - 7.1.3 Age (less than 65 vs. 65 or older)
- 7.2 Following randomization, insurance pre-authorization will be obtained for the specified treatment modality. If a patient's insurance will not cover payment for the assigned treatment arm, that patient will be removed from the study and will be treated off protocol.
- 7.3 Radiation target definition for glioblastoma as follows. GTV defined as tumor cavity and any T1 tumor enhancement. CTV will include GTV + 2 cm margin customized to include FLAIR enhancement (if thought by the radiation oncologist to be tumor) and exclude bone, fascia, and other anatomical barriers. PTV-50 will include CTV + 3-5 mm and will be treated to 50 Gy in 30 fractions. PTV-60 boost volume will include GTV + 3-5 mm and will be treated to 60 Gy in 30 fractions.
- 7.4 For patients randomized to IMRT, treatment will be planned using Pinnacle software system. Planning will be based on non contrast CT images obtained at time of simulation in addition to MRI scan. Treatment will be delivered using linear accelerator. Fractionated radiation will be delivered daily M-F with weekends off for all patients. IMRT plans use a configuration of five to seven isocentric 6-MV photon beams delivered in a step-and-shoot technique. For inverse planning specified dose constraints are given to organs at risk including the brainstem, spinal cord, optic chiasm, optic nerves, and cochlea.
- 7.5 For patients randomized to IMPT treatment planning will be conducted using the Varian Eclipse system. The same target delineation and expansions will be used as detailed above for IMRT. Treatment will then be delivered using the 250 MeV synchrotron (Hitachi Ltd. Power Systems, Ibarakiken, Japan) at the Proton Therapy Center at MD Anderson Cancer Center. Treatments will be delivered as once daily fractions, 5 days per week M-F with weekends off for all patients. IMPT may be planned using either multi-field optimization or single field optimization depending on the individual patient case. In single field optimization each field is optimized to deliver the prescribed dose to the target volume. Multi-field optimization uses simultaneous spot optimization and has been previously described [42]. Additionally if passive scatter is utilized. physical aperatures or compensators are utilized to modify the intensity of the beam. Beam angles are similar to those used for 3D proton therapy. For purposes of inverse planning specified dose constraints are used for organs at risk as in IMRT planning. The RBE for proton irradiation is set at 1.1. Thus the dose unit, Gy (RBE) is proton dose in Gy x RBE of 1.1.
- 7.6 Dose limitations to critical structures. Below is a list of dose constraints to critical structures. Every effort should be made to achieve these normal tissue constraints.

2013-0097 March 1, 2019 Version 15 Page 14

V60Gy<0.01cc and V55Gy <0.5cc and V30 <33%
V30Gy<50%
Max dose<54Gy
Max dose<45Gy and mean < 30 Gy
Max dose<45Gy and mean < 30 Gy
Max dose<40Gy and mean < 30 Gy
Max dose<40Gy and mean < 30 Gy
Max dose<5Gy
Max dose<5Gy
Max dose<54Gy
Max dose<54Gy
No defined dose constraint. See below.

In addition, bilateral hippocampal contours will be manually generated on the fused planning MRI CT image set by the treating physician. These contours should be generated as performed in RTOG 0933.

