11.0 Criteria for Removal from the Study

- 11.1 Analysis will be by intention-to-treat and those patients who withdraw from the study after randomization, but prior to receiving treatment will be tracked to ensure there is no bias introduced into the study.
- 11.2 Patients who do not complete the assigned treatment will be recorded and followed. These patients can be treated by best medical therapy as per the judgment of the treating physicians.

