12.0 Statistical Considerations

- 12.1 Randomization procedure: A stratified block randomization procedure will be used. Randomization will be performed using CORe. The randomization strata are as defined above in section 7.0, and the block size will be 6. Patients who withdraw from the study after randomization, but prior to receiving treatment will be considered a cancel and replaced.
- 12.2 Sample size: With IMRT the cognitive function failure rate at 4 months is 45%, based off of comparative analyses of the cognitive failure rate of RTOG 0614 and compared to the cognitive impairment seen on RTOG 0525; we hope to demonstrate that IMPT can achieve a cognitive function failure rate at 4 months of only 30%. We assume the time to cognitive failure in each treatment arm follows an exponential distribution. A cognitive failure rate of 45% at 4 months then implies a median time to cognitive failure of 4.6 months, while a cognitive failure rate of 30% at 4 months implies a median time to cognitive failure to cognitive failure of 7.8 months.

We will use a 1-sided significance level of 0.20 as suggested by Rubinstein et al. [51]for phase II screening trials. We expect to enroll 2 patients per month, and we will randomize 60 evaluable patients (30 to each treatment arm). We will have 80% power to detect an improvement in cognitive failure at 4 months from 45% in the IMRT arm to 30% in the IMPT arm. We expect to observe 43 events, and the analysis will be performed once we have observed these events. We define evaluable patients as those who have received the assigned treatment *and* completed baseline and at least one follow-up neurocognitive testing. We expect we will need an over accrual of 33% to account for those patients not evaluable. Therefore the target total enrollment sample size is 90 patients to accrue a total of 60 evaluable patients. We expect to observe 43 events, and we expect the trial to take 41 months to observe these events.

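### Insurance is checked after randomisation, for the assigned arm only, and removing denied patients cannot be squared with an intention-to-treat analysis that scores them as failures

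*Combined protocol and SAP*

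**What the plan says.** Section 7.2 fixes the timing and scope of the insurance check: "Following randomization, insurance pre-authorization will be obtained for the specified treatment modality". The consequence of a denial follows: "If a patient's insurance will not cover payment for the assigned treatment arm, that patient will be removed from the study", with treatment then given off protocol. Coverage is not an eligibility criterion. Section 6.6 and the checklist leave suitability for both modalities to the radiation oncologist.

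Other sections bear on the same patient:

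- Section 12.1: "Patients who withdraw from the study after randomization, but prior to receiving treatment will be considered a cancel and replaced".
- Section 11.1 states an intention-to-treat analysis and says that those who leave between randomisation and treatment "will be tracked to ensure there is no bias introduced into the study".
- Section 11.2: "Patients who do not complete the assigned treatment will be recorded and followed".
- Section 12.2: "We define evaluable patients as those who have received the assigned treatment", and who also have baseline and at least one follow-up cognitive test. Also: "Therefore the target total enrollment sample size is 90 patients to accrue a total of 60 evaluable patients".
- Section 12.3 makes the primary analysis intention-to-treat and counts non-evaluable patients as treatment failures. It gives no date for such a failure.
- Section 12.4 repeats the primary analysis in evaluable patients and plans as-treated versions of most analyses.

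On timing of the analysis, 12.2 expects 43 events and says "the analysis will be performed once we have observed these events".

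**The concern.** Randomisation protects a comparison only if what happens afterwards does not decide who is counted. Here a post-randomisation event tied to the assigned modality decides it. Section 5.1 says that IMPT costs more, so unequal denial is plausible, though not documented.

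The text then leaves open which analysis follows:

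- **Denied patients are dropped.** The primary set is a modified intention-to-treat set. The comparison is biased if denial is related to cognitive outcome, in either direction.
- **Denied patients are kept and scored under 12.3.** A refusal by an insurer, or a missing test, is counted as cognitive decline. That penalises the arm with more denials.

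The stated purpose in 10.1.1 is to isolate the effect of radiation on cognition. Neither route serves it well, and nobody reading the plan can say which will be used.

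**Working it through.** **1. Can the passages be reconciled?** Take a patient randomised to IMPT and refused cover before the first fraction.

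- Removal (7.2), replacement (12.1) and tracking (11.1) can all be carried out together. Applying 12.1 assumes that withdrawing includes being removed.
- Under 12.2 the patient is non-evaluable, because the assigned treatment was not received. Under 12.3 a non-evaluable patient in the intention-to-treat analysis is a treatment failure.
- Cancelling the patient and scoring the patient as failed are incompatible, and no passage says which governs.
- Treatment failure is not one of the event types in 12.3 (cognitive failure, progression, death), so the scored event has neither a date nor a clear type.
- Section 8.2 lets baseline testing run into the first 5 fractions, so a patient refused before treatment may have no baseline score.

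**2. The plan's own figures (12.2).** Inputs: 4-month failure 45% and 30%, exponential times, one-sided 0.20, power 80%.

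- Hazard ratio = ln(0.70)/ln(0.55) = 0.597; medians 4.64 and 7.77 months.
- Events = 4 × (0.8416 + 0.8416)² / (ln 0.597)² = 11.33/0.267, which rounds up to 43. Power at 43 events is 0.803.
- Enrolment = 60/(1 − 0.33) = 90, or 45 months at 2 per month. The 60 evaluable patients then arrive at 4/3 per month, giving 42.9 expected events at 41 months with competing risks ignored.

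The design figures reproduce.

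**3. Denied patients removed and replaced.** Assume a fraction f of IMPT is denied, a gap d in 4-month failure between denied and retained patients, and no true effect. The retained IMPT rate is 0.45 ∓ f × d. With f = 0.20 and d = 0.20 it is 0.41 or 0.49, and simulated type I error is about 0.34 or 0.11. With f = d = 0.10 it is 0.44 or 0.46, giving about 0.23 or 0.17. If denial is unrelated to outcome it stays at 0.20.

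**4. Denied patients scored as failures.** Section 12.2 places non-evaluable patients on top of 30 evaluable per arm. With k denied and scored by 4 months, failure is (k + 9)/(30 + k) in IMPT, since 0.30 × 30 = 9, and (k + 13.5)/(30 + k) in IMRT, since 0.45 × 30 = 13.5.

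| k | IMPT, k denied | Difference, IMPT-only denials (IMRT 45%) | IMRT, k denied | Difference, equal denials |
|---|---|---|---|---|
| 3 | 36.4% | 8.6 points | 50.0% | 13.6 points |
| 6 | 41.7% | 3.3 points | 54.2% | 12.5 points |
| 9 | 46.2% | −1.2 points | 57.7% | 11.5 points |

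Simulated power for failure dated at time zero (unadjusted log-rank, competing risks ignored; about 0.80 with no denials):

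| Layout | k | IMPT-only denials | Equal denials |
|---|---|---|---|
| Additional to 30 per arm, 43 observed events, 45-month accrual | 3, 6, 9 | 0.66, 0.49, 0.35 | 0.78, 0.77, 0.75 |
| Among the 30, scored failures count towards 43 | 3, 6, 9 | 0.59, 0.37, 0.16 | 0.73 to 0.75, 0.67, 0.61 |

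Dating the failure at 4 months softens this. On the second layout, IMPT-only power becomes 0.71, 0.63 and 0.54.

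**5. Effect of the test used.** Section 12.3 specifies Fine and Gray, not a log-rank test. A check with a Fine-Gray-type score test, on the second layout and an assumed competing hazard of 0.05 or 0.10 per month in both arms, gave power of 0.67 or 0.62 before any denial. The levels above are therefore optimistic; the direction is unchanged.

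**The case against.** The strongest reply is that a coherent reading exists. Section 7.2 is the only rule that names insurance. Pre-treatment leavers are removed, replaced and tracked, and only later non-evaluable patients count as failures. The evaluable-only and as-treated analyses would expose any distortion, and no denial rate is documented.

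Much of this stands. A reader might infer that the plan holds four or five mutually contradictory rules. It does not: removal, replacement and tracking are compatible, and stretching 11.2 to someone who never started treatment is strained. What remains is that the coherent reading is modified intention-to-treat, while 11.1 and 12.3 state intention-to-treat. The supplementary analyses do not define the primary set, and both depart from the randomised groups.

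Three stronger inferences are tempting, and the documents do not support them:

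- **That the trial is already biased in a known direction.** Section 7.2 applies to both arms, no denial rate is given, and removal is harmless if denial is unrelated to outcome. Adjustment for RPA class, MMSE and age would also absorb any part that runs through them.
- **That failure scoring inflates type I error.** This needs more denials in IMRT. That is the less plausible direction, because 5.1 calls IMRT the institutional standard and IMPT the costlier option.
- **That up to 30 of the 43 events could be scored rather than observed.** The 30 planned non-evaluable patients cover every cause, not insurance alone. Some would have had progression or death first, which 10.1.1 treats as competing events. The figure is an upper bound.

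**Conclusion.** The concern holds as a defect in the primary analysis set and in the timing of the coverage check. It is not evidence of bias that has occurred. Retention depends on the assigned arm by the terms of 7.2, and the plan does not settle whether a randomised patient who is refused cover is cancelled or counted as a cognitive failure.

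The size depends on assumed denial rates. On the reading closest to 12.2, three IMPT-only denials scored at time zero take power from 0.80 to about 0.66, and nine take it to about 0.35. Equal denials cost only 2 to 5 points (0.78 to 0.75). Failure dated at 4 months costs less, so the missing date in 12.3 matters in its own right. These figures assume exponential times, an unadjusted log-rank test and no competing risks.

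This should be fixed, because modest text changes remove the ambiguity.

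**What to change.** 1. **Sections 6.6, 7.2 and 13.1.** For patients not yet randomised, confirm coverage for both modalities before randomisation, as part of the existing pre-randomisation review. Complete baseline cognitive testing before randomisation where possible.
2. **Sections 7.2, 11.1 and 12.1.** Reconcile them so that every randomised patient stays in the assigned arm for analysis, with cognitive follow-up where the patient agrees, whatever treatment is received.
3. **Section 12.3.** In the primary analysis, do not score non-receipt of the assigned treatment or absence of tests as cognitive failure. Score failure from all available tests against baseline, with progression or death first as competing events. Report patients with no usable test by arm and reason, and do not call the resulting set full intention-to-treat. Keep failure scoring as a sensitivity analysis, beside others that allow for informative dropout, because censoring at the last test assumes that dropout is uninformative.
4. **Section 12.2.** State that the 43 events are observed cognitive failures.

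The rules should be fixed before outcomes are compared by arm.

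**Cost.** The change needs an amendment and two coverage requests per patient; the documents do not say whether insurers will pre-authorise both modalities. Results would apply to patients covered for both. Retained patients who receive the other modality dilute the effect: if 10, 20 or 30% of IMPT patients receive IMRT, power is about 0.75, 0.69 or 0.63 (30 per arm, 43 events, log-rank).

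Accrual slows. If a fraction f of candidates lacks coverage for one modality, confirming both takes 45/(1 − f) months: about 50, 56 or 64 for f = 10, 20 or 30%. The present rule, with replacement and IMPT-only denials, takes 45/(1 − f/2): about 47, 50 or 53. This assumes that cancelled patients do not count towards the 90, which the plan does not say.

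The text is Version 15, dated March 2019, and gives no accrual status. If accrual is complete, only items 3 and 4 still apply, with retention in the analysis of patients already tested.
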